**Table 5-5: First supplementary analysis data handling and missing data imputation strategy.**

Pattern ID	ICE and the associated reason	ICE strategy and data handling	Reference group for modeling the distribution of missing or unobservable data
1	Intake of prohibited medications	Hypothetical strategy If participant did not take prohibited concomitant medication.	Participants, from the same arm, who comply** with treatment regimen and have observed data at the time point that requires imputation.
	Any reason	Discard the collected data after the intake of prohibited medication(s) for a certain time frame based in the medication class (See Section 6.5.3 for details).	
2	Temporary treatment interruption*  Due to COVID-19/ administrative or any other treatment unrelated reasons	Hypothetical strategy If participant complied with treatment.  Data collected for a specific assessment during/after a temporary treatment interruption will be discarded for that assessment Week only.	Participants, from the same arm, who have available data before and during the treatment interruption.  MI will be used to model change from a time point before treatment interruption to a time point with treatment interruption (Copy Increment from Reference imputation strategy).
3	Permanent treatment	Treatment policy/Hypothetical	Missing values that occur after the ICE will be

	discontinuation  Due to AE/lack of efficacy	strategy  If participant remained untreated/on background therapy after permanent discontinuation of the randomized treatment, use the treatment policy strategy and utilize the collected data.  Otherwise, if participant initiated an alternative treatment, use the hypothetical strategy under the hypothetical scenario “If participant did not initiate an alternative treatment after permanent discontinuation of randomized treatment”. Discard data after the ICE.	imputed using a similar MI model as used in the main analysis of the primary endpoint, i.e., the MI regression model will include auxiliary variables indicating (yes/no) whether the participant continued on randomized treatment at each visit ( Guizzaro et al., 2021 ).
4	Permanent treatment discontinuation  Due to COVID-19/ administrative or any other treatment unrelated reasons	Hypothetical strategy If participant did not discontinue the randomized treatment due to the specified reason.  Any data collected after permanent treatment discontinuation will be discarded.	All other participants from the same arm (i.e., participants without a similar ICE at the time point that requires imputation).

\*If more than one interruption for different reasons is recorded during the specified weeks (please see the definition of ICE in Section 1.1), the data handling rule and missing data imputation will be performed based on the reason in the following pre-specified order: 1) AE, 2) Due to COVID-19/ administrative or any other treatment unrelated reasons.

\*\* Complying with treatment regimen is defined as having no ICEs (i.e., no early discontinuation of randomized treatment, no treatment interruption in the respective week (definition in [Table 1–2](#)) and no intake of prohibited concomitant medications.

Missing values that occur in the time frame outside of any identified ICE and simply represent missed assessments will be assumed missing at random (MAR). Such missing values are likely to be intermittent and will be imputed using a Monte Carlo Markov Chain (MCMC) MI method for imputation of non-monotone missing data. Additional details are provided in Section 6.3.

A pattern-mixture model using multiple imputation will be applied to impute missing and unobservable data to mimic the distribution of observed data in the appropriate reference group as described in [Table 5–5](#), conditional on covariates and partially observed data. The imputations will be done sequentially in patterns 1 through 4. The reference group for imputation in patterns 3 and 4 may contain participants who have some values imputed during the imputation of preceding patterns. Consequently, the MI model for pattern 4 will reflect a mixture of participants, some of which fully comply with the randomized treatment and some with other types of ICEs. Additional details of the pattern-mixture modeling with multiple imputation are provided in Section 6.3.

Each imputed dataset will be analyzed using the MMRM model specified in [Table 5–3](#) to obtain an estimate of the treatment effect. The results will be combined using the Rubin’s rule ([Rubin, 1987](#)) to obtain an overall estimated treatment effect.

The same baseline covariates will be included in the imputation and the analysis step as specified in Section 5.3.1.

The results from the supplementary analysis will be presented in a similar way as to the main analysis (see Section 5.3.1).

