**Table 5–4: First Supplementary Estimand: ICEs and Strategies to address them**

ICEs**	Reason for ICE	Strategy	Data handling method
Temporary Treatment interruption*	AEs (treatment related/unrelated)	Treatment policy	Utilise the collected data after ICE.
	COVID-19 and administrative reasons	Hypothetical, If participant complied with treatment.	Model outcomes during the ICE under the hypothetical scenario.
Permanent discontinuation of randomized treatment	AEs (treatment related/unrelated) or Lack of efficacy		
	For participants who remained untreated/on background therapy.	Treatment policy	Utilise the collected data after ICE.
	For participants who initiate alternative VMS treatment	Hypothetical, If participant remained untreated.	Model outcomes after the ICE under the hypothetical scenario.
	Other treatment-unrelated reasons, including COVID-19	Hypothetical, If participant did not discontinue the randomized treatment.	Model outcomes after the ICE under the hypothetical scenario.
Intake of prohibited concomitant medication having impact on efficacy	All reasons	Hypothetical, If participant did not take prohibited concomitant medication.	Model outcomes under the hypothetical scenario during the period of confounding.

ICE=Intercurrent event, AE=Adverse event, VMS = Vasomotor symptoms

\*Definition of temporary treatment interruption:

Week 1 = Treatment taken on <5/7 days during week 1.

Week 4 = Treatment taken <80% during weeks 1-4 OR treatment taken on <5/7 days during either week 3 or 4.

Week 8 = Treatment taken <80% during weeks 1-8 OR treatment taken on <5/7 days during either week 7 or 8.

Week 12= Treatment taken <80% during weeks 1-12 OR treatment taken on <5/7 days during either week 11 or 12.

\*\*ICEs will be reviewed prior to the study unblinding.

The details of data handling and missing data imputation for the first supplementary analysis of the primary endpoints are summarized in the [Table 5–5](#). A pattern-mixture model using multiple imputation (MI) will be used to impute missing or discarded values that occur in presence of ICEs in a way that aligns with the ICE strategies.

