**Table 5–7: Second supplementary estimand data handling and missing data imputation strategy.**

Pattern ID	ICE and the associated reason	ICE strategy and data handling	Reference group for modeling the distribution of missing or unobservable data
NA	Intake of prohibited medications	Composite strategy Treatment failure (i.e., no improvement from baseline.)	N/A
	Any reason	Discard the collected data after the intake of prohibited medication(s) for a certain time	

		frame based in the medication class (See Section 6.5.3 for details) and assign the value of zero change from baseline.	
1	Temporary treatment interruption  Due to COVID-19 /administrative or any other treatment unrelated reasons	Hypothetical strategy  If participant complied with treatment.  Data collected for a specific assessment during/after a temporary treatment interruption will be discarded for that assessment Week only.	Participants, from the same arm, who comply** with treatment regimen and have observed data at the time point that requires imputation. (same as the first supplementary analysis)
2	Temporary treatment interruption  Due to AE	Treatment policy strategy  Utilize all the collected data in the analysis.	Participants, from the same arm, who have available data before and during the treatment interruption.  MI will be used to model change from a time point before treatment interruption to a time point with treatment interruption (Copy Increment from Reference imputation strategy). (same as the first supplementary analysis)
3	Permanent treatment discontinuation  (Due to AE/lack of efficacy)	Treatment policy strategy  If participant remained untreated/on background therapy after permanent discontinuation of the randomized treatment, use the treatment policy strategy and utilize the collected data.	Missing values that occur after the ICE will be imputed using a similar MI model as used in the main analysis of the primary endpoint, i.e., the MI regression model will include auxiliary variables indicating (yes/no) whether the participant continued on randomized treatment at each visit (Guizzaro et al., 2021). (same as the first supplementary analysis)

		Composite strategy  Otherwise, if participant initiated an alternative treatment, use the composite strategy assuming treatment failure (i.e. no change from baseline). Discard data after the ICE and impute with participant's baseline value.	N/A

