**Impute missing values occurring during an ICE associated with pattern 2.**

A multiple imputation regression model will be used to model change from a time point before treatment interruption to a time point during treatment interruption as the dependent variable (change equal to pre-interruption value minus value at the time point of interruption). The model will include as predictors the baseline value, value before treatment interruption, and the fixed, categorical effects of treatment and region. Because the number of participants in this pattern is expected to be small, modeling of change in outcome from pre-interruption to during interruption will be done by pooling data across time points where treatment interruptions occur. Missing values at a time point  $k$  will be replaced by subtracting the change value predicted by the imputation model from the participant’s value at the time point  $(k-1)$  prior to treatment interruption.

This step will be implemented with PROC MI and MONOTONE REG statement explicitly specifying the model described above. The input dataset will include all participants in pattern 2 and participants with temporary interruption due to treatment unrelated reasons from pattern 1 who have observed data before and during the interruption.

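### As it reads in the available text, SAP Table 5-5 pattern 2 imputes a complied-with-treatment scenario from women who interrupted treatment, in conflict with Tables 5-4 and 5-7 and Section 6.3

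*SAP*

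**What the plan says.** SAP Table 5-4 defines the first supplementary estimand. For temporary interruptions due to COVID-19 or administrative reasons the strategy is hypothetical, and the data handling is "Model outcomes during the ICE under the hypothetical scenario". Interruptions due to adverse events follow treatment policy. The introduction to Section 5.3.3 says the hypothetical strategy for treatment-unrelated interruptions applies in both supplementary estimands.

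Table 5-5 turns this into imputation rules. Its pattern 2 covers interruptions for COVID-19, "administrative or any other treatment unrelated reasons". The scenario is "If participant complied with treatment". The discard rule is "Data collected for a specific assessment during/after a temporary treatment interruption will be discarded for that assessment Week only". The reference group is "Participants, from the same arm, who have available data before and during the treatment interruption", and the model is described as "MI will be used to model change from a time point before treatment interruption to a time point with treatment interruption", labelled Copy Increment from Reference.

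Table 5-7, for the second supplementary estimand, lists the same event as pattern 1 with this reference group: "Participants, from the same arm, who comply with treatment regimen and have observed data at the time point that requires imputation". It keeps the before-and-during group for its own pattern 2, interruptions due to adverse events under treatment policy. Both rows are marked as identical to the first supplementary analysis.

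Section 6.3 gives the implementation steps for both tables. Pattern 1 is imputed from participants who complied. The input data for the pattern 2 step include "participants with temporary interruption due to treatment unrelated reasons from pattern 1 who have observed data before and during the interruption".

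**The concern.** A reference group should represent the scenario being imputed. For these women that scenario is compliance, yet the Table 5-5 row learns from women who were not taking treatment as planned. If the donors interrupted because of adverse events, their outcomes are assigned to women who are meant to be modelled as compliers. If the donors interrupted for treatment-unrelated reasons, the analysis puts back the kind of data it has just discarded.

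Followed literally, the row would make the first supplementary analysis miss its stated estimand for this event. The two supplementary analyses would also handle the same event differently while the SAP says they match. Section 6.3 sends the programmer to Tables 5-5 and 5-7 for the pattern definitions, so the wording of the row can determine what is coded.

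**Working it through.** The documents give no figure for this point, so the check is a comparison of passages.

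**Treatment-unrelated interruption**

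| Place in SAP | Pattern | Target | Reference group |
|---|---|---|---|
| Table 5-4 | – | Outcome had she complied | – |
| Table 5-5 | 2 | Outcome had she complied | Women with data before and during an interruption |
| Table 5-7 | 1 | Outcome had she complied | Compliers |
| Section 6.3 | 1 | Missing and discarded values | Compliers |

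**Adverse-event interruption**

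| Place in SAP | Pattern | Target | Reference group |
|---|---|---|---|
| Table 5-4 | – | Treatment policy | – |
| Table 5-5 | No visible row | – | – |
| Table 5-7 | 2 | Treatment policy | Women with data before and during an interruption |
| Section 6.3 | 2 | Missing values only | Women with data before and during an interruption |

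1. The footnote to Table 5-5 defines compliance as having no intercurrent event, including no interruption in the week concerned. A woman contributing data during an interruption is therefore not a complier at that week, and the Table 5-5 scenario and reference group exclude each other.

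2. In Section 6.3 the headings for patterns 1, 3 and 4 cover both missing and discarded values. The pattern 2 heading covers missing values only. That suits treatment policy, where nothing is discarded, and does not suit Table 5-5 pattern 2, where data are discarded. Read strictly, no step fills those discarded values.

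3. In Table 5-5, pattern 1 is prohibited medication only. The reference in Section 6.3 to treatment-unrelated interruptions in pattern 1 fits Table 5-7 and does not fit Table 5-5.

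4. The increment model itself is the same in Table 5-5 and Section 6.3. The disagreement is about whom it applies to and whether it replaces discarded data.

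**Size.** Section 6.3 imputes the value at week k as the participant's previous value minus a predicted change, conditional on her baseline and pre-interruption values. Write δ for the resulting mean excess over the value expected under compliance, given the same history, and f for the share of an arm imputed this way at Week 12. Then, approximately:

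shift in an arm's mean = f × δ

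shift in the treatment difference = f_E × δ_E − f_P × δ_P (E elinzanetant, P placebo)

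Neither f nor δ is in the documents. Purely as an illustration, the elinzanetant arm alone would shift by:

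- f = 1%, δ = 0.5 hot flashes/day: 0.01 × 0.5 = 0.005
- f = 5%, δ = 1: 0.05 × 1 = 0.05
- f = 10%, δ = 2: 0.10 × 2 = 0.20

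The last case is extreme. A δ of 2 equals the largest treatment difference in SAP Table 3-1, whereas the flag needs only intake on fewer than 5 of 7 days or below 80%. An equal shift on placebo cancels: 0.05 − 0.05 = 0.

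**Power.** With 270 per arm and SD 4.29, the standard error is 4.29 × √(2/270) = 0.369. The noncentral t at one-sided 0.025 gives 77.1%, 98.2% and 99.97% for differences of 1.00, 1.50 and 2.00, as the SAP states. None of these depends on the disputed row.

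**The case against.** The strongest objection is that the table text is damaged and the rule is not wrong. Tables read from PDF can lose or merge rows. Table 5-7 says its adverse-event row matches the first supplementary analysis, and the Table 5-5 footnote ranks adverse events first among interruption reasons. Both presuppose an adverse-event row that is not visible in Table 5-5. A pattern 1 reference cell spanning two events, followed by a collapsed adverse-event row, would produce the text we see. This stands as a real possibility and is why the source PDF must be checked first. Against it, the pattern 2 row reads as complete: event, scenario, discard rule, reference group and model are all present.

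A second objection is that Tables 5-4 and 5-7 and Section 6.3 already settle the rule. They do show what was probably intended. They do not cure the row, because Section 6.3 refers back to Table 5-5 for its pattern definitions.

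A third is that a raw gap between interrupters and compliers, multiplied by a share of one arm, overstates the effect. That is right: the model conditions on each woman's own earlier values, and the reported quantity is a difference between arms.

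**Conclusion.** The conflict is real in the text as available. If Table 5-5 is printed this way, the row needs correcting, because following it would impute interruption outcomes for a compliance scenario. Its reach is limited to the first supplementary analysis. The size is unknown, since the documents give no interruption rates. It is probably small, because only women flagged for treatment-unrelated interruption are involved. Section 6.3 expects few participants in pattern 2, but on its own numbering those are the adverse-event interruptions, so this is only indirect support.

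A reader might infer three stronger things that the documents do not support:

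- **That the primary result is compromised.** The main estimand uses treatment policy for every intercurrent event, so the primary analysis, its alpha and its power do not depend on this row.
- **That the sponsor deliberately chose interrupters as donors, or left adverse-event interruptions without a rule.** Table 5-4 assigns those interruptions treatment policy, Tables 5-4 and 5-7 and Section 6.3 point to the complier reference for the others, and the absent row may be a conversion loss.
- **That the bias can be quantified.** The figures above are single-arm illustrations on assumed inputs, not estimates.

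**What to change.** Check Table 5-5 against the source PDF. If it is printed as it reads here:

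- Give treatment-unrelated interruptions the complier reference group, as in Table 5-7 pattern 1 and the first step of Section 6.3.
- Show adverse-event interruptions as a separate row under treatment policy, with the before-to-during increment model used only for values that are actually missing, as in Table 5-7 pattern 2.
- Use the same pattern numbers in Tables 5-5 and 5-7 and Section 6.3.

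The repair uses the SAP's own rules and needs no new data. Before unblinding it costs a correction to one table and its cross-references. If the programs are already written, the sponsor should also record which rule they implement.

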The rows of [Table 5–5](#) represent various patterns (subsets) of participants with a specific type of an ICE. For participants from each pattern who have missing data during the time frame of the ICE (see Sections [6.5.1](#) and [6.5.3](#) for the description of time frame for intake of prohibited medication and temporary treatment interruption ICEs. The time frame for the permanent

treatment discontinuation is defined as the time after discontinuation) or unobservable data under the assumed hypothetical scenario, a reference group is specified in the last column of the table.

Available data of participants from the corresponding reference group will be used to model the distribution of missing and unobservable data in each pattern. For the baseline value to be imputed, at least 2 post-baseline values out of the 4 post-baseline values (i.e. Week 1, 4, 8 & 12) need to be available. In case there are less than 10 participants with available post-ICE data in the defined reference group, at any intermediate time point, the missing data for that pattern will not be imputed at that time point. Additional details are provided in Section [6.3](#).

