### 5.3.3.2 Second Supplementary Analysis

The details of the second supplementary estimand can be found in Table 5–6 and Table 5–7. Similar analysis steps (i.e., imputation, modeling and combining results) as for the first supplementary analysis will be applied to the secondary supplementary analysis (see Section 5.3.3.1).

For the intake of prohibited medication and permanent treatment discontinuation after which participants initiated alternative VMS treatments, the composite strategy will be used to handle the data. The attributes for this estimand are the same as the main estimand except for following:

- Variable: Change in frequency of moderate to severe HF from baseline to Week 12 in the absence of ICEs (i.e. intake of prohibited medication or initiation of alternative VSM treatment after permanent discontinuation of randomized treatment) or no change from baseline otherwise.
- Intercurrent Events (ICEs): see Table 5–6.

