**Table 6–3: Preliminary list of alternative VMS treatment by drug grouping (can be updated during blind review meeting)**

DGCODEL0	DGNAME0	DGCODEL1	DGNAME1	DGCODEL2	DGNAME2	Duration of impact with respect to efficacy* (considered up to 12 weeks**)
		5	Hormone replacement therapy	2	Oestrogens	1, From 1st dose to 4 weeks after the last dose if the route is vaginal, intravaginal, cutaneous, nasal or transdermal. 2, From 1st dose to 8 weeks after the last dose if the route is oral, sublingual or intrauterine, 3, From 1st dose to 12 weeks or longer if the route is subcutaneous or intradermal.
		5	Hormone replacement therapy	3	Progestogens	1, From 1st dose to 4 weeks after the last dose if the route is vaginal, intravaginal, cutaneous, nasal or transdermal. 2, From 1st dose to 8 weeks after the last dose if the route is oral, sublingual or intrauterine, 3, From 1st dose to 12 weeks or longer if the route is subcutaneous or intradermal.
1633	Drugs for psychiatric disorders	111	Antidepressants	113	Selective serotonin reuptake inhibitors (SSRI)	From 1st dose to 4 weeks after the last dose

\*In this column, the terms "1st dose" and "last dose" both refer to the start date and stop date of certain doses of concomitant medication. If the dose was changed, a new start date and/or stop date were reported.

\*\* No further differentiation if duration of impact is longer than 12 weeks since ICEs are considered in the analysis only for the first 12 weeks of the study.

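### Pattern 3 of both supplementary analyses starts discarding at the stop of study drug, while other SAP text points to the first dose of the alternative VMS drug

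*SAP*

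**What the plan says.** Several parts of the SAP set the start of the discard at the stop of study drug:

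- In Table 5-5, pattern 3, the ICE column holds permanent discontinuation for adverse event or lack of efficacy. If the woman began an alternative treatment, the instruction is "Discard data after the ICE".
- Section 5.3.3.1, just before Table 5-5, gives the time frame of this ICE: permanent "treatment discontinuation is defined as the time after discontinuation".
- Section 5.1.2 flags the discontinuation ICE from the week of the stop, or from the next week if the stop falls on the 6th or 7th day.
- Table 5-7, pattern 3, has the same row for the second analysis: "Discard data after the ICE and impute with participant's baseline value".

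Other parts point to the alternative drug:

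- The scenario in Table 5-4 for these women is "If participant remained untreated".
- Section 5.3.3 speaks of discontinuation together with the start of an alternative VMS treatment. The variable of the second estimand in Section 5.3.3.2 names "initiation of alternative VSM treatment after permanent discontinuation of randomized treatment" as the event.
- Table 6-3 gives each alternative VMS drug group a duration of impact that begins at its first dose, for SSRIs "From 1st dose to 4 weeks after the last dose". Table 6-4 does the same for a named drug.
- Pattern 1 of Table 5-5 (prohibited medication) starts at intake: "Discard the collected data after the intake of prohibited medication(s) for a certain time frame based in the medication class".

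For its time frames, Section 5.3.3.1 refers to Sections 6.5.1 and 6.5.3. It does not refer to Section 6.5.2, where Tables 6-3 and 6-4 stand.

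**The concern.** In the first supplementary analysis, the weeks between stopping study drug and the first dose of another drug are observations of exactly the scenario being modelled. They are neither missing nor unobservable, which are the two conditions Section 5.3.3.1 gives for imputation. The same off-drug weeks are kept for a woman who never starts another drug. Her own untreated values would also help predict the later weeks that do need imputing, because the pattern 3 model in Section 6.3 uses values at previous time points. Discarding them also lowers the number of women with post-discontinuation data, and that model drops its on/off-treatment indicator at an intermediate time point when fewer than 10 such women remain.

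In the second analysis, the same pre-initiation weeks are scored as treatment failure before the event that Section 5.3.3.2 defines as failure has happened.

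Two programmers could also start the discard at different dates. The drug groups in Table 6-3 reappear in Table 6-5, and the drug in Table 6-4 reappears in Table 6-6, so one dose can trigger both pattern 1 and pattern 3 with different start points. Imputing patterns 1 to 4 in sequence fixes an order of computation. It does not say which pattern governs her data.

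**Working it through.** **Inputs.** Week 1 is Days 2-8, Week 4 is Days 22-28 and Week 12 is Days 78-84 (Section 5.1.2.1); Week 8 is Days 50-56 (Table 1-2). An event on days 1-5 of a week flags that week; on day 6 or 7 it flags from the next week (Section 5.1.2). ICEs are flagged from randomization to Day 84.

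**Step 1: apply the flag rule to both start points.** The SAP writes the rule for discontinuation and prohibited intake; here it is also applied to the first alternative dose. The alternative drug is taken as continuing, so its impact window is still open at Week 12.

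| Stop day | First alternative dose | Lost, counting from stop | Lost, counting from first dose | Untreated values lost |
|---|---|---|---|---|
| 20 | 60 | Weeks 4, 8, 12 | Week 12 | Weeks 4, 8 |
| 24 | 50 | Weeks 4, 8, 12 | Weeks 8, 12 | Week 4 |
| 30 | 82 | Weeks 8, 12 | Week 12 | Week 8 |
| 30 | 83 or 84 | Weeks 8, 12 | none | Weeks 8, 12 |
| 40 | 100 | Weeks 8, 12 | none | Weeks 8, 12, if a start after Day 84 counts |

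First row: Day 20 is day 6 of Week 3, so the flag starts at Week 4. Day 60 is day 4 of Week 9, so the flag starts at Week 9.

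**Step 2: all pairs by Day 84.** Days 2 to 84 with first dose after stop give 83 x 82 / 2 = 3,403 pairs. In 69% at least one untreated value at Weeks 4, 8 or 12 is lost. In 162 of them (162 / 3,403 = 4.8%) the loss includes Week 12, always with a first dose on Day 83 or 84. Equal weight on pairs is a device for seeing which visits are hit, not a forecast.

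**Step 3: short course, first analysis only.** Example: stop Day 10, SSRI from Day 20 to Day 40. The impact ends on Day 40 + 28 = Day 68, before Week 12 opens on Day 78. Counting from the stop removes Weeks 4, 8 and 12. Counting from first dose with the Table 6-3 window removes Weeks 4 and 8 only.

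**Step 4: scale.** The SAP's power figures reproduce: with N = 270 per arm, SD 4.29 and one-sided 0.025, the noncentral t gives 77.1%, 98.2% and 99.97% for differences of 1.0, 1.5 and 2.0, against the stated 77.1%, 98.2% and >99.9%. The planning SE is 4.29 x sqrt(2/270) = 0.369 hot flashes per day. None of these figures depends on the pattern 3 rule.

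If a fraction f of one arm has a Week 12 change of size d wrongly replaced by zero, that arm's mean moves by f x d. The documents give neither f nor d. Assuming f = 0.5% to 3% and d = 2 to 6 per day, the shift runs from 0.005 x 2 = 0.01 to 0.03 x 6 = 0.18 per day, or 0.03 to 0.49 of the SE. This applies only to the narrow Week 12 cases, and equal shifts in both arms cancel in the difference.

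**The case against.** The strongest reply is that the SAP already means initiation. Sections 5.3.3 and 5.3.3.2 tie the event to starting the other drug, the sentence in Table 5-5 before the discard instruction concerns initiation, and Table 6-3 would have little purpose otherwise. That is a fair reading of intent. It does not displace the ICE column, the time-frame sentence in Section 5.3.3.1 or the flag rule, which all run from the stop.

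A reader might infer that untreated Week 12 values are routinely lost, for example through a first dose at Week 30. The documents do not support that. Section 5.1.2 and the Table 6-3 footnote confine ICEs to the first 12 weeks. If that limit also governs initiation, late starts change nothing. It is not settled, because initiation only sub-classifies a discontinuation that itself falls by Day 84, treatment status is recorded for everyone who discontinues (Section 6.5.2), and no cut-off for initiation is stated.

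A reader might also infer that zero change at Week 12 in the second analysis is an artefact. For a woman who initiates by then it is what the composite variable prescribes. Only visits before initiation are in question.

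Lastly, re-imputation with on/off-treatment indicators may cost mainly precision. That holds if women who start another drug resemble, given the model's predictors, those who stay untreated; the documents cannot show whether they do.

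**Conclusion.** The point holds as a mismatch between estimand and data handling in two supplementary analyses. The operative wording starts at the stop of study drug; the scenario, the composite variable and the impact windows point to the other drug. The values at risk are mainly untreated Weeks 4 and 8. Week 12 is lost needlessly only with a first dose on Day 83 or 84 (if the flag rule applies to initiation), with a start after Day 84 if that counts, or, in the first analysis, after a short course.

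The main treatment-policy analysis uses all collected data and is unaffected. The number of women is likely small. The effect on the Week 12 contrast is modest and cannot be quantified from the documents; the range in the working rests on assumed inputs. Wrongly zeroed Week 4 or 8 values should move the Week 12 contrast little once all visits are filled; this is reasoned, not simulated. The assumed 10% drop-out should not be read as 60 women with off-drug diaries, because it is used to reduce 300 to 270 per arm for the endpoint.

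**What to change.** Before unblinding, amend the SAP as follows.

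- **Table 5-5, pattern 3:** discard only weeks flagged from the first dose of the alternative VMS drug to the end of its duration of impact in Tables 6-3 and 6-4, using the week-flag rule of Section 5.1.2. Use values collected while untreated after the stop.
- **Table 5-7, pattern 3:** assign zero change from the week flagged for initiation onwards, and use earlier off-drug values as collected. Do not end the zeroing with the duration of impact. Table 5-6 applies a period of confounding to prohibited medication but the whole time after the ICE to alternative treatment, so ending it early would change the composite estimand.
- **Section 5.3.3.1, time-frame sentence:** add the start point above and state that only initiation up to Day 84 alters the handling of Weeks 1-12.
- **Precedence:** state whether pattern 1 or pattern 3 governs when the same drug triggers both.

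The cost is wording in two table rows and a short addition to Section 5.3.3.1, plus the matching programming. No new data are needed: Protocol Section 6.8 requires start and end dates of medication, and Section 7.1 requires documentation of medication used after discontinuation.
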